**Version Number: 1.0**  
**01 March 2017**

**STATEMENT OF COMPLIANCE**

The study will be conducted in compliance with the protocol, International Conference on Harmonisation [ICH] E6, applicable regulatory requirements, and carried out in accordance with Good Clinical Practice (GCP) as per the following:

- Health Canada Health Products and Food Branch [HPFB] Regulations
- Tri-Council Policy Statement: Ethical Conduct for Research Involving Humans, Canadian Institutes of Health Research, Natural Sciences and Engineering Research Council of Canada, Social Sciences and Humanities Research Council of Canada
- Personal Information Protection and Electronic Documents Act, Bill C-6 [PIPEDA]
- USA Food and Drug Administration [FDA] Code of Federal Regulations [CFR] applicable to clinical studies (45 CFR Part 46; 21 CFR Part 50, 21 CFR Part 56, and 21 CFR Part 312)
- <http://www.hhs.gov/ohrp/humansubjects/guidance/45cfr46.htm#46>  
<http://www.fda.gov/cder/guidance/959fnl.pdf>  
<http://www.cancer.gov/clinicaltrials/learning/page3>.
- National Institute of Health (NIH) Clinical Terms of Award;  
<http://grants.nih.gov/grants/guide/notice-files/NOT-OD-01-061.html>

All key personnel (all individuals responsible for the design and conduct of this study) have completed GCP/Human Subjects Protection Training.

## LIST OF ABBREVIATIONS

AE	Adverse Event/Adverse Experience
CFR	Code of Federal Regulations
CIOMS	Council for International Organizations of Medical Sciences
CRF	Case Report Form
CT	Computerized tomography
EM	Electromagnetic
FDA	Food and Drug Administration
FDG	Fluoro-deoxyglucose
GTV	Gross Tumour Volume
GTV-endo	Gross Tumour Volume - Endoscopic
GTV	Gross Tumour Volume - Standard
IGRT	Image Guided Radiation Therapy
IMRT	Intensity Modulated Radiation Therapy
MRI	Magnetic resonance imaging
NIH	National Institutes of Health
OAR	Organ at Risk
OCI	Ontario Cancer Institute
OHRP	Office for Human Research Protections
PET	Positron emission tomography
PI	Principal Investigator
PIPEDA	Personal Information Protection and Electronic Documentation Act
PHIPA	Personal Health Information Protection Act
PMH	Princess Margaret Hospital
REB	Research Ethics Board
RMP	Radiation Medicine Program
SAE	Serious Adverse Event/Serious Adverse Experience
SOP	Standard Operating Procedure
STAPLE	Simultaneous Truth and Performance Level Estimation
UHN	University Health Network

## PROTOCOL SUMMARY

Title	Comparison of Endoscopic Visualization and CT Imaging of Head and Neck Cancers with Pathological Validation
Population	
 
• Age <math>\geq</math> 18 years
 
• Histologic diagnosis of squamous cell carcinoma
 
• Primary H&N cancer
 
• Disease visible on endoscopy
 
• Intention to treat definitively using radical surgery therapy.
 

Number of Sites	One – Princess Margaret Cancer Centre, Toronto, Ontario
Study Duration	Accrual over 18 months years.
Description of Intervention	CT imaging immediately prior to surgery. Biopsy sampling of tissue samples using tracking and navigation technologies to register biopsy sampling to CT images
Objectives	
Primary Objectives:
 
 
• Pathological assessment of superficial extent of disease beyond CT-visible disease
 
• Comparison of Gross Tumour Volume contours to pathological findings
 

Description of Study Design	This is a single centre, single arm feasibility study
Estimated Time to Complete Enrollment:	10 patients total, over 1.0 years

## 2 BACKGROUND AND RATIONALE

### 2.1 Head and Neck Radiotherapy

Approximately half of cancer patients require radiation therapy (RT)\* at some point during their care. Technological advances in RT, such as intensity modulation (IMRT) and image guidance (IGRT), allow radiation dose delivery with high accuracy and millimeter precision. RT planning can be thought of as a serial, step wise chain-like process where each link depends on the previous one. As these technical links are improved and strengthened, accurate definition of the target is now emerging as the weakest step in the RT process. Accurate target definition is fundamental to all subsequent treatment planning and delivery and is critical for successful RT. Incorrect target definition can result in poorer outcomes through either undercontouring (less tumour control), overcontouring (more normal tissue toxicity), and/or both. For head and neck (H&N) cancer, the role of various combinations of radiological imaging in target delineation has been investigated with respect to target delineation at depth. However, contouring with only standard radiological methods often misses superficial disease when compared to pathological sampling.

For head and neck cancers, endoscopy is invaluable in visualizing the superficial, radiographically occult extent of disease. Relation of these findings to the planning environment, however, is based primarily on the treating clinician's recall of the endoscopically visible disease relative to anatomical landmarks, a process subject to substantial contouring bias, error, and uncertainty in delineating the target or gross tumour volume (GTV).

Endoscopic examination of involved endothelial surfaces plays a critical albeit qualitative role in target delineation revealing superficial visible tumour extending beyond the invading disease apparent on volumetric imaging studies. In current practice, the clinician integrates the endoscopic findings into the treatment plan using their clinical judgment, recollection of anatomical landmarks and experience to define a target volume. Although clinical practice may vary, permanent records of the endoscopic procedure such as screen captures are not typically stored in the medical record. The subjectivity of this practice is evident in the large inter-observer variations observed in most contouring studies that include the physical exam.

### 2.2 Spatially Registered Endoscopy

To address these issues and improve contouring of superficial disease, we have designed and prototyped a novel platform that uses endoscopic tracking and image analysis tools for the accurate registration of endoscopic images to the treatment planning CT. Disease visible on endoscopy can then be contoured and registered to the planning CT, allowing inclusion of superficial disease invisible on the volumetric CT image dataset into the treatment plan.

Specifically, contouring can be performed on 2D endoscopic images, projected into 3D image space and imported into the treatment planning software. Our "optical simulation" (or endoscopic contouring) technology employs 3 fundamental technologies: an optical imaging

system, tracking technology, and image registration software. These technologies have been integrated into a single platform developed primarily for image-guided surgery which has been used in other REB-approved trials. The optical systems used in our initial studies were flexible endoscopes typically used in patient physical exams. Both real and virtual endoscopic images can be simultaneously displayed or, using various transparent display techniques can be overlaid on each other. Orthogonal views are also displayed showing the camera coordinates and contours.

The endoscopic contouring was demonstrated in pilot clinical studies with accuracies of ~3 mm on patients each with early stage (T1) glottic cancer. Endoscopic imaging was performed shortly after acquisition of the planning CT images. Patients were examined in the same position as the CT imaging, including fixation mask. Video and tracking information was recorded, allowing retrospective analysis. The 15 minute procedure was well tolerated by all subjects. Clinicians reviewed the video for frames displaying the tumour. Concordance between the endoscopic contours and those generated by the CT images alone were excellent along the superficial extent of the disease.

These cases were selected deliberately to be visible on both the optical and CT imaging, providing confirmation of contour concordance and as proof of concept. In contrast to this protocol, no suspicious submucosal extension was allowed in these patients. The study concluded optical simulation was feasible in these patients.

We currently have a clinical trial examining the impact on contouring accuracy by including spatially registered endoscopic imaging to the planning CT. Despite limited enrollment, several of the cases have shown large discrepancies between the CT visible GTV and the GTV contoured when endoscopic information is included.

The proposed study will examine the necessity of endoscopic contouring by comparison with pathology in a limited number of patients with oral cancer that are scheduled for surgical resection. Using image-guided surgery tools very similar to those used in the endoscopic contouring, we will compare GTV delineation of H&N cancers with and without the use of endoscopic contouring to pathologic findings. The study will use resources available in the GTx-OR (described below) to perform endoscopic contouring on oral cancer patients during the surgical procedure, immediately prior to resection.

The resected samples will be processed using whole mount pathology methods. Images of the whole mount tissue sections will be registered with the CT images acquired before and during surgery so that the pathology findings can be spatially correlated with the CT and endoscopic imaging. The pathology findings will also aid in defining the superficial extent of the disease and if these findings correlate with the region defined by the endoscopic imaging.

### **3 Objectives**

#### **3.1 Primary Objectives**

- 3.1.1 To compare the location of lesions visible on the tissue surface with standard CT imaging and pathology

#### **3.2 Secondary Objectives**

- 3.2.1 To determine the registration accuracy of spatially navigated endoscopy in a controlled surgical setting.

### **4 Study Design**

#### **4.1 Overview**

- 4.1.1 This is a single centre, single arm feasibility study comparing target delineation of GTV for H&N cancer to pathology using either standard CT-based contouring or spatially registered endoscopy combined with CT-based contouring.
- 4.1.2 Oral cancer surgery will be performed under image-guidance, including a standard contrast-enhanced CT scan immediately prior to the resection procedure. This CT scan will replicate the standard radiation planning CT scan and will be used for delineation of the GTV-std. External fiducial markers will be placed on the patient for registration of the navigation tools to the CT image coordinate system.
- 4.1.3 During surgery, the superficial lesion will be mapped using either a standard pointing tool that will be used by the surgeon to outline the lesion or navigated endoscopy will be performed of the superficial disease visible in the oral cavity. The endoscopic video will be spatially registered to the prior CT scan and used post-procedure for endoscopic contouring as an aid in delineation of the GTV.
- 4.1.4 The tissue will be marked along all planned excisions and resected using standard protocols. The surgical specimen will be mounted and scanned fresh in the OR using the CT scanner and a small animal MRI for correlative pathology. The sample will be prepared for whole mount pathology mapping by embedding the fixed tissue in a gel. The sample will be imaged again using the small animal MRI. It will then be delivered to pathology whole-mount section and identification of disease margins, both superficial and at depth. Details of the pathology workflow are in Section 7.6.
- 4.1.5 Following the procedure, contouring of the GTV will be performed by a radiation oncologist unfamiliar with the surgery and using only the CT image. The mapping

of the superficial lesion (from 4.1.3) will be added to the CT image and the errors between the standard CT-based contouring and the extent of the superficial lesion will be measured. The standard contours and lesion mapping will be compared to pathology for concordance and volume.

[figure not shown]

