## **4.2 Integration with Standard Treatment of H&N Cancer**

- 4.2.1 The patient will undergo standard clinical assessment and preparation for surgical resection of oral lesions.
- 4.2.2 A standard contrast-enhanced CT scan will be added to the standard surgical procedure, with fiducial markers placed on the patient's skin and with the patient in same position as used during surgery.
- 4.2.3 During the surgery, the superficial disease will be delineated using either a pointing tools tracking the outline of the tumour or using navigated endoscopy. The delineated disease will be registered to the initial CT scan using fiducial markers placed on the patient prior to the CT scan.
- 4.2.4 Patients will receive standard treatment for oral H&N cancer with surgery according to the UHN H&N oncology site policies. Treatment will not be modified based on the results of this study.
- 4.2.5 The radiation oncologist(s) will use the intra-operative CT scan to delineate the GTV as per standard clinical practice.
- 4.2.6 The overlap and differences between the mapped superficial disease and the GTV will be measured.
- 4.2.7 The locations of the disease identified by the CT scanning and the superficial lesion mapping will be correlated with the pathology reports. (See Sections 7.2 and 7.6 below for details)

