### 7.2 Design & Methodology

- 7.2.1 Using the Somatom FLASH CT scanner in the OR, a contrast-enhanced CT scan using standard Radiation Medicine protocols will be performed minus the use of a head fixation mask. The contrast agent will be Visipaque. The patient will be awake and generally positioned as they would be for the surgery/endoscopy procedure. Fiducial markers will be added to the patient's surface to be used for the registration of the endoscopy to the CT imaging.
- 7.2.2 The patient will be transferred to the operating table that is part of the ZEEGO robotic imaging device. In this transfer, the Zeego table is rotated and extended so that it aligns with the table of the CT scanner tables. A thin carbon fiber board under the patient is lifted and the patient moved to the Zeego table. A similar procedure has been used in other protocols in the GTx OR.
- 7.2.3 Patient is prepared for surgery.
- 7.2.4 Prior to tumour excision, surgeon defines the observable superficial extent of the disease one of two methods, determined at the discretion of the surgeon. One option uses a tracked pointing tool to record its position as the surgeon moves the pointer around the outline of the superficial disease. The other option is to use navigated endoscopy to record video of the superficial disease. (See Section 7.5) The endoscopes used here can be either rigid (with optical tracking) or flexible (using EM tracking)
- 7.2.5 The surgical procedure will continue using standard of care. Immediately prior to resection of the visible tumour, the tissue will be marked to identify visible extent of the superficial disease and the added margin. The navigated endoscopy will be repeated so that it includes these markings.
- 7.2.6 After surgical resection, a cone-beam CT scan will be acquired to define the location of the resected tissue. The cone-beam CT scan will be registered to the pre-resection CT scan for comparison of the resected volume and the disease contoured by the radiation oncologists. (See 7.2.9 below).

- 7.2.7 The resected tissue sample will be imaged again using a small field of view MRI scanner (0.5T) located in the OR. The tissue sample will then be sent to pathology for standard assessment. See Section 7.6 below for details of pathology handling.

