### **7.4 Equipment and Software for Endoscopic Contouring**

- 7.4.1 The navigation tools and image guidance software platform used in this protocol have been developed within UHN. The tools include real-time optical and electromagnetic tracking (using commercially available equipment from NDI, Waterloo, ON) of surgical instruments and endoscopes co-registered to CT and MR imaging and display of the imaging information using augmented visualization methods. The necessary functions include:

- reading of CT images and data,
- tracking of EM sensors, calibration of endoscopic images,
- registration of CT image and EM coordinate spaces,
- registration of video images to CT images,
- selection of video frames for contouring,
- contouring on endoscopic images and

- export of endoscopic contours for reading by the treatment planning system.

7.4.2 This package has been demonstrated in several previous and current REB protocols:

UHN REB 11-0660-CE, Localized Intraoperative Virtual Endoscopy (LIVE) for Surgical Guidance in Sinus and Skull Base Patients

UHN REB 12-5315: The Translational Research Image-Guided Operating Room (TRIGORA): Intraoperative 3D Imaging for Head & Neck Surgical Patients

UHN REB 13-5914-C: Comparing Target Delineation of Head and Neck Cancers With and Without the Aid of Spatially Registered Endoscopy

UHN REB 15-9147-CE: Intraoperative 3D Imaging and Navigation for Patients with Benign Bone Tumours

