## 7.5 Endoscopy Procedures

7.5.1 The endoscopy procedure will follow the CT scan and patient transport, which will be within 30-40 minutes following the CT scan. If necessary, immobilization devices may be used to fix the patient in the same position for endoscopy as used during the CT scan. Small plastic fiducial markers will be temporarily added to the patient using double sides tape. Once the patient is in place on the surgical table, CT to EM registration will be performed. The fiducial markers placed on the patient will be identified and located in both the CT image and in real space using the EM secondary pointing tool.

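### The CT reader is kept unaware of the surgery, but nothing keeps the map of the superficial lesion independent of the study CT

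*Protocol*

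**What the plan says.** Section 3.1.1 compares the location of lesions visible on the tissue surface with CT and pathology. Sections 4.1.5 and 4.2.6 turn this into a measured difference between the CT-based contour and the mapped superficial lesion. Section 7.7.2 compares each of the two with pathology.

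On the operation itself, 4.1.2 states: "Oral cancer surgery will be performed under image-guidance, including a standard contrast-enhanced CT scan immediately prior to the resection procedure". Section 7.5.1 adds: "Once the patient is in place on the surgical table, CT to EM registration will be performed". Section 7.4.1 describes tracked instruments and endoscopes "co-registered to CT and MR imaging and display of the imaging information using augmented visualization methods". Section 2.2, describing the same platform in general terms, says real and virtual endoscopic views can be shown side by side or overlaid, and continues: "Orthogonal views are also displayed showing the camera coordinates and contours".

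On the mapping, 7.2.4 says: "Prior to tumour excision, surgeon defines the observable superficial extent of the disease one of two methods, determined at the discretion of the surgeon". The options are a tracked pointer whose position is recorded, or navigated endoscopy recorded as video. Section 4.1.3 has the video contoured after the procedure, and 7.2.9 registers the mapped lesion to the CT.

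On masking, 4.1.5 has the GTV contoured by a radiation oncologist who does not know the surgery and works from the CT alone. Section 7.2.8 places that contouring after surgery.

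**The concern.** A difference between two measurements of the same lesion can be read as a difference between methods only if neither was made with the other in view. The protocol accepts this for the CT contour and does not apply it to the lesion map.

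A surgeon who can see where the tracked tool lies on the contrast-enhanced CT may, without intending to, let the enhancing region settle a doubtful edge. Someone outlining a video frame beside the registered CT may do the same. The map would then drift towards the CT. Sections 4.1.5 and 4.2.6 would show a smaller difference than direct vision or endoscopy alone would give, and the two overlaps with pathology in 7.7.2 would move closer together. The superficial disease beyond the CT-visible tumour, which the study sets out to find, is what would be understated.

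The independence is lost, if at all, while the map is being made. No later analysis can restore it.

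**Working it through.** The protocol gives no figure for this point, and no arithmetic applies. The check sets the sections side by side.

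1. **Is independence needed?** Yes, for the lesion map. It is compared with the CT contour in 3.1.1, 4.1.5 and 4.2.6, and with pathology alongside the CT contour in 7.7.2. GTV-endo is a different matter: 7.7.1 defines it as CT and endoscopy combined, so it depends on the CT by design and is outside this point.

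2. **Is the CT reader masked to the map?** Yes, by 4.1.5.

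3. **Could the surgeon see the CT while mapping?** The sequence allows it. The CT is taken first (7.2.1), the patient is moved to the operating table (7.2.2), CT-to-tracker registration follows (7.5.1), and the lesion is mapped before excision (7.2.4). The navigation tools include "display of the imaging information using augmented visualization methods" (7.4.1). Nothing in 7.2.4 says whether that display is on or off.

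4. **What could be seen at that moment?** Only the CT image. The GTV contours are drawn after surgery (7.2.8), so the surgeon cannot be copying the contour with which the map is compared.

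5. **Does the endoscopy option differ?** Yes. The surgeon films, and the outline is drawn later (4.1.3). The main exposure therefore moves to whoever draws it. That person is not identified and no masking is stated. The protocol does not fix whether this happens before or after the GTV contouring in 7.2.8, so both the CT and the GTV-std contours could be in view.

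6. **Does the map need the CT on view while it is made?** No. Section 7.2.4 asks only for recorded positions or video, and 7.2.9 provides for registering the map to the CT. Section 2.2 describes contouring on the two-dimensional endoscopic image and then projecting it into three dimensions. The functions that 7.4.1 lists as necessary do not include a live CT display for the surgeon.

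7. **Could carry-over be detected afterwards?** Not from the planned data. The study accrues at most 10 patients (9.1.1), the mapping method is left to the surgeon (7.2.4), no comparison of mapping with and without the CT in view is planned, and the data list in 7.8 does not record what was displayed.

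**The case against.** The strongest reply is that the protocol already directs mapping by sight. Section 7.2.4 asks for the extent that can be observed, with pointer or endoscope used to record, and the map can be placed on the CT afterwards. Sections 2.2 and 7.4.1 describe what the platform can do, not what is shown at that step. Section 2.1 gives the rationale that superficial disease is often hidden on imaging, so a raw CT may offer little to copy. The surgeon also knows the diagnostic imaging in any case. And this is a feasibility study of up to 10 patients, with pathology as the reference for both methods.

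Much of this stands. A reader might infer from 4.1.2 that the surgeon maps with the study CT on the screen and that CT information does enter the map. No section says either. The documents support an open possibility and no more.

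A reader might also see a conflict between image guidance and the statement in 4.2.4, "Treatment will not be modified based on the results of this study". That does not hold. The sentence concerns the study's results, which are comparisons of contours, map and pathology made after resection, and 4.2.2 openly adds the CT to the procedure.

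The reply does not remove the asymmetry. An instruction to map what is observable is not masking. The protocol did not rely on instruction alone for the CT reader, for whom it spelled out what may be known and used. Pathology as a common reference does not help either, because a map drawn towards the CT would share the CT's errors against pathology.

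**Conclusion.** The point holds as an unguarded risk. The protocol masks the CT reader to the surgery. It does not state whether the surgeon, or the person who outlines the video, is masked to the study CT, although the set-up allows the CT to be shown.

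The size cannot be estimated: the documents contain no data on mapping with and without the CT in view, and any figure in millimetres would have to be invented. The likely direction, towards the CT and so towards a smaller CT-map difference, is a judgement about how people draw doubtful edges. It is not something the documents show.

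The point deserves action because it touches the primary comparison, cannot be repaired in analysis and costs little to close.

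**What to change.** - In 7.2.4, state that the CT or virtual view is not shown to the surgeon while the lesion is traced or filmed for research. Tracking data and video are recorded and projected onto the CT afterwards, under 7.2.9.
- In 4.1.3 or 7.2.9, state who outlines the superficial lesion on the video. That person should work on the video frames without sight of the CT or the GTV-std contours, and finish before projection. GTV-endo can still be built afterwards with the CT in view.
- In 7.8, add an entry for each patient recording whether the CT was in view during the mapping in 7.2.4 and during the tissue marking in 7.2.5. For 7.2.5 this is a record only: it should not restrict what the surgeon may consult when marking the resection.

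The cost is a few sentences, a display turned off during the research mapping, and one more item on the data sheet. The surgeon will still know the earlier diagnostic imaging, so independence is improved but not complete, and the report should say so.
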